4.4 Estimands

4.4.1 Primary estimands

The primary estimand #1 is defined by the following attributes:

- Population: Adult patients hospitalized for Acute Respiratory Distress Syndrome, as defined by the inclusion-exclusion criteria of the study.
- Variables: Oxygenation index (OI) at baseline and at day 7.
- Intercurrent events:
 - Death before Day 7, or at Day 7 if OI is not present, as a terminal event which precludes the observation of the variable, will be handled by the composite strategy. Day 7 value is derived using Study Day based on Date (i.e., Day 7= First IMP Intake + 6), since only date of death is collected. The event will be included in the estimand by imputing for OI at day 7, an extreme unfavorable value characterizing the treatment failure. The 90°

Standard/Forms/Template				
Title		Statistical Analysis Plan Template		
Code		Version	Effective Date	Page
PPD		01	29 Aug 2022	28 of 78

percentile of the distribution of the observed values will be used (the value will be rounded to present only one decimal place only for data presentation, not for imputation).

- For patients that at day 7 are extubated and OI is not evaluable, extubation will be handled by the composite strategy as an event which precludes the observation of the variable of interest. The event will be included in the estimand by imputing for OI at day 7 a sufficiently extreme favorable value characterizing the treatment success. The 10° percentile of the distribution of the observed values will be used (the value will be rounded to present only one decimal place, only for data presentation, not for imputation). A patient is extubated at day 7 if the patient results not intubated in the time range [First IMP Intake Date/Time +132h, First IMP Intake Date/Time +155h and 59 min].
- Treatment discontinuation, which may affect interpretation of the variable, will be handled by the treatment policy strategy. The occurrence of the intercurrent event will be irrelevant. All observed values will be used regardless of occurrence of the intercurrent event. Retrieved dropouts will be used for data imputation of all missing data (not due to death and not due to extubation), whichever is the reason of missingness.
- Population-level summary: Change in oxygenation index (OI) from baseline to day 7

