Estimand #1: Difference in means between Reparixin and Placebo in the change in oxygenation index (OI) from baseline to Day 7 in adult patients hospitalized for Acute Respiratory Distress Syndrome, as defined by the inclusion-exclusion criteria of the study, regardless of treatment discontinuation whatever the reason and alive up to day 7, intubated at Day 7.

The primary estimand #2 is defined by the following:

- Population: Adult patients hospitalized for Acute Respiratory Distress Syndrome, as defined by the inclusion-exclusion criteria of the study.
- Variables: Ventilator free days (VFD) at day 28.
- Intercurrent events:
 - Death before or on Day 28, as a terminal event which precludes the complete observation of the variable, will be handled by the composite strategy. The event will be included in the estimand with an extreme unfavorable value (0) characterizing the treatment failure.
 - Treatment discontinuation, which may affect interpretation of the variable, will be handled by the treatment policy strategy. The occurrence of the intercurrent event will be irrelevant. All observed values will be used regardless of occurrence of the

Standard/Forms/Template				
Title		Statistical Analysis Plan Template		
Code		Version	Effective Date	Page
PPD		01	29 Aug 2022	29 of 78

intercurrent event. Retrieved dropouts will be used for data imputation of all missing data (not due to death), whichever is the reason of missingness.

- Population-level summary: Mean VFD at day 28.

Estimand #2: Difference in means between Reparixin and Placebo in Ventilation Free Days (VFD) at Day 28 in adult patients hospitalized for Acute Respiratory Distress Syndrome, as defined by the inclusion-exclusion criteria of the study, regardless of treatment discontinuation whatever the reason and alive at day 28.

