For the imputation of Day 7 missing data, rules described in section 0 will be applied, and following the estimand definition, for missingness due to treatment discontinuation or any other reason (whichever the reason), MI-RD regression model will be created by including treatment, OI baseline value (imputed as described in this section), gender and age class (<65, >=65 years) as covariates (further details about the MI process are described below).

If there are not enough retrieved dropouts for convergence of MI-RD regression model, the Copy Reference approach will be used using OI baseline value, gender and age class (<65, >=65 years) as

Standard/Forms/Template				
Title		Statistical Analysis Plan Template		
Code		Version	Effective Date	Page
PPD		01	29 Aug 2022	43 of 78

covariates. Imputation of values in the two treatment arms will be done using the non-missing values from all the patients in the control group. The final decision on the use of the MI-RD vs Copy-Reference will be done at the time of the analysis and reported in the CSR.

Whether for MI-RD or Copy-Reference approach, the adjusted estimated changes from baseline for each treatment arm together with the corresponding 95% confidence intervals will be shown. The difference between Reparin and placebo in the change from baseline at Day 7 will be displayed together with the corresponding two-sided 90% confidence interval (in order to reflect the one-sided 95% confidence intervals). One-sided p-value (alpha=0.05 one-sided) will also be displayed for descriptive purpose.

MI process will be implemented as follows:

STEP1: Run MI for OI baseline missing data on 1000 imputations using:

CCI

Use numeric variable in the MCMC model.

At the blinded DRM, a discussion on the pattern of missingness will be held and it will be evaluated if data show a monotone pattern. If it will be evaluated that no monotone pattern is there, the statement “impute=monotone” will be deleted from the SAS code.

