STEP 2: A MI-RD for Day 7 missing data will be performed on the output datasets created in step 1 (with “nimpute=1”). A thousand datasets will be generated. The random seed number will be CCI. Missing OI data at Day 7 will be imputed using the specified MI regression model. MI regression model will include treatment, OI baseline value (as described in step 1), gender and age class (<65, >=65 years) as covariates. According to MI-RD approach, only non-missing values from retrieve dropouts will be used to inform the MI regression model.

STEP 3: Derive change from baseline (using imputed/non imputed data).

STEP 4: Each of the 1000 datasets with observed and imputed data will be analyzed using the ANOVA model.

STEP 5: Rubin’s rule will be used for combining results to draw inference.

Standard/Forms/Template				
Title		Statistical Analysis Plan Template		
Code		Version	Effective Date	Page
PPD		01	29 Aug 2022	44 of 78

7.1.1.2 VFD at day 28

Summary statistics will be provided for the variable and by subgroups defined in section 4.5. For the estimand definition, please refer to section 4.4.1, while for the derivation of the endpoint please refer to section 11.1.1.

VFD at day 28 will be analysed using an ANOVA model as described in section 7.1.1.1 (considering as covariates: treatment, gender and age class (<65, >=65 years)).

If convergence is not reached or the Estimated G-matrix is not positive definite in at least one of the models after imputation, the random effect will be dropped.

Check of the normality assumption will be performed on the observed data, before applying imputation process.

If assumption of normality is not confirmed (see section 4.1) analysis on original scale will be kept. An additional supplementary analysis on log-transformed data will also be performed (see section 7.1.3.4).

For the imputation of ventilatory free days missing data at day 28, rules described in section 0 will be applied, and following the estimand definition, for missingness due to treatment discontinuation or any other reason (whichever the reason), MI regression model will include treatment, gender and age class (<65, >=65 years) as covariates. A thousand data sets will be generated. The random seed number will be **CCI**. MI will be implemented in the following steps:

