Retrieved drop-out flag for change in OI from baseline to day 7	
For "change in OI from baseline to day 7" the retrieved dropouts are the patients that discontinued the study treatment (treatment completers/discontinuers are defined above in this table under "Treatment completed/discontinued") by day 7 *(day 7 not included) and have the endpoint evaluable by Day 7 (death on the day of the treatment discontinuation not part of the retrieved dropout):
 
Set to 'Y' if Subject discontinued the treatment prematurely by day 7* and patient is alive or have date of death after end of treatment, and the endpoint is not missing for this parameter and timepoint.
 
* date of discontinuation should be prior to the min value for the range of time windows of day 7 (study day using date/time) i.e., discontinuation should happen before First IMP Intake+132h.

Standard/Forms/Template				
Title		Statistical Analysis Plan Template		
Code		Version	Effective Date	Page
PPD		01	29 Aug 2022	62 of 78

Parameter	Calculation

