Retrieved drop-out flag for ventilatory free days at day 28	
For "VFD at Day 28" the retrieved dropouts are the patients that discontinued the study treatment (treatment completers/discontinuers are defined above in this table under "Treatment completed/discontinued") and have the endpoint evaluable by Day 28 (death on the day of the treatment discontinuation not part of the retrieved dropout):
 
Set to 'Y' if Subject discontinued the treatment prematurely and patient is alive or have date of death after end of treatment, and the endpoint is not missing for this parameter and timepoint.

Standard/Forms/Template				
Title		Statistical Analysis Plan Template		
Code		Version	Effective Date	Page
PPD		01	29 Aug 2022	63 of 78

Parameter	Calculation
Change in oxygenation index (OI) from baseline to day 4 [study day based on Date/time]	
The endpoint is derived similarly to change from baseline at day 7.
 
 - If patient dies before Day 4, or at Day 4 (Day 4 date = Day 1 date + 3, since only date of death -no time- is collected) and OI is missing: OI at day 4 = 90th percentile of the distribution of the primary variable at Day 4. - If patient at Day 4 is extubated* and OI is not evaluable (i.e., if the patient results not intubated* in the time range [First IMP Intake Date/Time +60h, First IMP Intake Date/Time +83h and 59 min]), OI at day 4 = 10th percentile of the distribution of the primary variable at Day 4. - Otherwise, OI is set to missing. 
*intubation/extubation status at day 4: check intubations in "Extubation Summary" CRF form. Use the multiple entries of extubation/re-intubation: if the last record of intubations/extubations prior day 4 is an extubation, and there are no intubations at day 4, it means the subject was extubated on Day 4.

ICU stay up to Day 28 and up to hospital discharge (days)	The information on ICU length of stay is collected under "Other Clinical Event Form" at Day 28 Visit and at Hospital Discharge Visit

Standard/Forms/Template				
Title		Statistical Analysis Plan Template		
Code		Version	Effective Date	Page
PPD		01	29 Aug 2022	64 of 78

Parameter	Calculation

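### Retrieved-dropout or Copy Reference imputation covers every missing co-primary value, including patients still on drug or who completed it, which goes beyond the protocol's scope

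*SAP*

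**What the plan says.** **Recipients.** For OI, SAP 4.4.1 sets "Retrieved dropouts will be used for data imputation of all missing data (not due to death and not due to extubation), whichever is the reason". For VFD it sets "Retrieved dropouts will be used for data imputation of all missing data (not due to death), whichever is the reason of missingness". SAP 4.10, 7.1.1.1 and 7.1.1.2 repeat the all-reasons scope. Treatment status is not a condition in any of them.

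**Donors.** SAP 7.1.1.1: "According to MI-RD approach, only non-missing values from retrieve dropouts will be used to inform the MI regression model". SAP 7.1.1.2 has the same rule. The donor flags are in SAP 11.1.1. For OI: "Set to 'Y' if Subject discontinued the treatment prematurely by day 7* and patient is alive or have date of death after end of treatment". For VFD: "Set to 'Y' if Subject discontinued the treatment prematurely and patient is alive or have date of death after end of treatment". Both also require a non-missing endpoint, and both exclude "death on the day of the treatment discontinuation not part of the retrieved dropout".

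**Fallback.** If too few retrieved dropouts exist for convergence, Copy Reference is used: "Imputation of values in the two treatment arms will be done using the non-missing values from all the patients in the control group". The choice between the two is made at the time of analysis.

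**Protocol.** Section 9.5.1.1 applies retrieved-dropout imputation to values missing because of intercurrent events. It defends Copy Reference on the ground that a reparixin patient who stops treatment is credited with no more than placebo's effect.

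**The concern.** Retrieved dropouts are a sensible source for patients who stopped treatment and then have no data. They are a poor source for a patient who is still taking the drug and whose ventilator reading or blood gas was simply not recorded. Under a treatment-policy strategy, that patient's missing value should resemble those observed in on-drug patients of the same arm.

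The donors also carry composite scores. A stopper who dies after the day of discontinuation holds a non-missing value (VFD 0, or the 90th percentile for OI), and an extubated stopper holds the 10th percentile for OI. A patient known to be alive and intubated in the Day 7 window has neither outcome, yet is drawn from a pool containing both. The OI imputation covariates (treatment, baseline OI, gender, age class) cannot separate these states.

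Under Copy Reference, a reparixin patient still on drug receives a placebo outcome. The protocol's argument for that concerns patients who have discontinued and does not reach this patient. The stake is the primary estimate of both co-primary endpoints, in a trial whose purpose is estimation.

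**Working it through.** **1. Who can be a recipient and who can be a donor (SAP 11.1.1).**

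- OI at a study day is not derived if either the mean airway pressure or FiO2/PaO2 is missing. This can happen to an intubated patient on full dosing. Such a patient is neither dead nor extubated, so the value goes to imputation.
- VFD is missing if the patient is alive and followed for fewer than 26 days. This can be a treatment completer. A patient whose treatment ended because of discharge home counts as a completer, so can be a VFD recipient but never a donor.
- OI donors must have stopped before 132 h and have a Day 7 value. Excluding only deaths on the day of discontinuation makes sense only if later deaths, with their scores, count as non-missing.
- Treatment is a covariate in the retrieved-dropout model, so the mismatch there is stopper versus on-drug, not arm versus arm. Under Copy Reference it is cross-arm for reparixin recipients only.

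**2. OI under retrieved-dropout imputation.** The plan gives no figure for this effect. Assumed: 90th percentile 22, 10th percentile 4, ventilated stoppers' mean 14, on-drug ventilated mean 12. With dead share d and extubated share e among donors:

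donor mean = 22d + 4e + 14(1 − d − e)

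| d | e | Donor mean | Error per imputed patient | Arm mean, 10% imputed |
|---|---|---|---|---|
| 0.20 | 0.10 | 4.4 + 0.4 + 9.8 = 14.6 | +2.6 | +0.26 |
| 0.50 | 0.10 | 11.0 + 0.4 + 5.6 = 17.0 | +5.0 | +0.50 |
| 0.20 | 0.30 | 4.4 + 1.2 + 7.0 = 12.6 | +0.6 | +0.06 |
| 0.10 | 0.30 | 2.2 + 1.2 + 8.4 = 11.8 | −0.2 | −0.02 |

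The sign depends on the mix. SAP 3.3 gives 5.35 points as the interval width for the OI difference.

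**3. VFD under retrieved-dropout imputation.** Suppose donors differ from completing survivors only by a dead share p at VFD 0. Each imputed survivor is then low by p × m, where m is the survivors' mean. Take p = 27% to 45% (the mortality range in protocol 2.6.2.3, borrowed as an assumption) and m = 12 to 20 days (assumed):

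- Per imputed patient: 0.27 × 12 = 3.24 to 0.45 × 20 = 9.0 days.
- Arm mean with 10% imputed: 0.32 to 0.90 days, against the SAP's interval width of 3.75 days.

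The between-arm effect needs unequal missingness. Assume 20% stop early, 25% of non-stoppers die, p = 0.45 and m = 16, with missing VFD in 20% versus 5% of surviving non-stoppers:

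0.80 × 0.75 × (0.20 − 0.05) × 0.45 × 16 = 0.65 days against the arm with more missing values.

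A null simulation on these inputs (33 per arm, survivor SD 7, recipients given the pooled stopper mean) moved the difference from −0.03 to −0.65 days. With 15% missing in both arms it moved from 0.01 to 0.03. Reversing the imbalance reversed the sign (from −0.03 to +0.61).

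**4. Copy Reference, OI.** If a share s of the reparixin arm is on drug and imputed at the placebo level, the difference becomes 6.6 × (1 − s), taking the 6.6 points that SAP 3.5.1 treats as a marker of clinical success:

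- s = 5%: 6.27
- s = 10%: 5.94
- s = 15%: 5.61

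Placebo recipients draw on their own arm, so missingness there does not offset this.

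**The case against.** **Unscored does not mean alive and intubated.** A reader might infer that every OI recipient is known to be ventilated, so scored donors are always wrong. SAP 11.1.1 does not support that: the extubation score requires the patient to reach Day 7. Someone extubated on Day 5 who withdraws on Day 6 is unscored, as is someone lost with vital status unknown. The scores are part of the composite outcome, so scored donors are appropriate for these patients. The objection stands and limits the measured-OI rule to patients known to be intubated.

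**Dead donors can be right for VFD.** A patient with missing VFD was last seen alive before Day 26, and Day 28 status is usually unknown. This stands. What remains for VFD is that completers are imputed from stoppers.

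**Direction and size.** A reader might infer that imputed OI is systematically too high. The last row of the table shows otherwise. A 50% dead share also exceeds the protocol's 27% to 45% mortality range, which is not a Day 7 figure, and a 15% on-drug missing share exceeds the 10% non-evaluable patients the plan expects. Effects on an arm mean are small beside the stated interval widths. All of this stands.

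**Already probed.** The SAP plans a missing-at-random sensitivity analysis (7.1.2.1), a complete-case analysis (7.1.3.1) and an analysis restricted to patients still intubated at Day 7 (7.1.3.6). Copy Reference is only a fallback, and its dilution works against reparixin. The trial specifies no hypotheses. These points lower the stakes, but none changes the primary estimator, and the missing-at-random analysis also draws on scored values.

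**Visibility.** The SAS code and two bullets of SAP 4.11 cannot be read here. The legible part of 4.11 does not list the wider scope as a change from the protocol; that is not proof that it went unrecorded.

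**Conclusion.** The concern holds on the text in a limited form. The SAP applies a method meant for missingness after discontinuation to all missing co-primary values, which is wider than protocol 9.5.1.1. The clear misfits are the on-drug patient known to be intubated at Day 7 with a missing component, and the treatment completer with missing VFD.

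Retrieved-dropout bias has no established size or sign. It depends on the donor mix and on differential missingness, neither of which the documents give. Between arms it is near zero if missingness is balanced and the donor-recipient gap is similar in both arms. Copy Reference has a known direction: the difference shrinks by the share of on-drug reparixin patients imputed, for example from 6.6 to 5.94 points at 10%, assuming the full effect applies to those patients. The documents do not support a claim that the result is biased in favour of reparixin, or that donors who died are wrong throughout.

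This should be changed because it affects the primary estimator and restores the protocol's scope, though the likely effect on the treatment difference is modest.

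**What to change.** In SAP 4.4.1, 4.10, 7.1.1.1 and 7.1.1.2, split the imputation by treatment status at the time point:

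- (a) Patients on drug at Day 7 (OI), or who completed treatment (VFD): impute within arm from on-drug or completer patients respectively.
- (b) Patients who stopped early: retrieved-dropout imputation, then Copy Reference, as now.
- (c) For OI only, where the patient is known to be alive and intubated in the Day 7 window: use only measured OI values as donors, in the primary analysis and in the missing-at-random analysis (7.1.2.1). Where vital or intubation status is unknown, keep scored donors.
- (d) State which rule applies to randomized-but-untreated patients. They are in the primary analysis set (SAP 4.2.3) but are neither on drug, completers nor stoppers.

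The cost is SAP wording and a grouping variable in the imputation code. The real downside is smaller donor pools. In a trial of about 66 patients, requiring measured OI from patients who stopped before 132 h makes non-convergence more likely and may send more stoppers to Copy Reference.

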4.10 Handling of missing and incomplete data

All reasonable efforts will be made to reduce the rate of missing data. Investigators will be trained about the importance of patient retention and full data capture. Also, any reasonable attempts should be made by the investigators to emphasize continued subject's participation for the full duration of the trial.

Patients who discontinue the treatment will not be withdrawn from the study by default, but will be asked to complete safety and efficacy observations as per the protocol, unless otherwise they withdraw their consent. Patients who discontinue study treatment and decide to remain in the study by following the schedule of assessments and continuing to adhere to protocol requirements are defined as "retrieved dropout" patients (section 11.1.1 provides details on the definition).

For the main analyses of the primary endpoints, missing data will be managed as follows:

- Missing data due to death, preventing the collection of the endpoint, will be imputed with an unfavourable value (see section 4.4.1).
- Missing data in extubated patient, preventing the collection of the endpoint (for Change in OI at Day 7 only), will be imputed with a favourable value (see section 4.4.1).
- Missing data due to treatment discontinuation or any other reason (whichever the reason) will be handled by means of Multiple Imputation (MI) approach as detailed in Section 7.1.1.

Sensitivity analysis of the primary endpoints can be based on different missingness assumptions (section 7.1.2.1)

In the descriptive summaries, the number of subjects with missing data will be presented under the "Missing" category. Missing values will be included in the denominator count when computing percentages. When continuous data will be summarized, only the non-missing values will be evaluated for computing summary statistics. Any exception will be declared.

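### Do the closing sentences of the two primary estimands confine them to survivors and, for the oxygenation index, to patients still intubated?

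*SAP*

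**What the plan says.** SAP 4.4.1 introduces the first estimand with "The primary estimand #1 is defined by the following attributes" and uses almost the same form for the second. The population attribute is the same in both: "Population: Adult patients hospitalized for Acute Respiratory Distress Syndrome, as defined by the inclusion-exclusion criteria of the study". It sets no condition on survival or ventilation after randomization.

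The intercurrent-event attributes are:

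- **Death, OI:** "The event will be included in the estimand by imputing for OI at day 7, an extreme unfavorable value characterizing the treatment failure". The value is the 90th percentile.
- **Extubation, OI:** "For patients that at day 7 are extubated and OI is not evaluable, extubation will be handled by the composite strategy". The value is the 10th percentile.
- **Death, VFD:** "The event will be included in the estimand with an extreme unfavorable value (0) characterizing the treatment failure".
- **Treatment discontinuation, both endpoints:** treatment policy, so observed values are used whether or not treatment was stopped.

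Each estimand then closes with a one-sentence statement. For OI it ends "regardless of treatment discontinuation whatever the reason and alive up to day 7, intubated at Day 7". For VFD it ends "regardless of treatment discontinuation whatever the reason and alive at day 28".

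**The concern.** The closing sentences carry the labels Estimand #1 and Estimand #2 and are the shortest statements of what the trial estimates. Read in the ordinary way, they limit the OI effect to patients alive and intubated at Day 7, and the VFD effect to patients alive at Day 28. Both are subsets formed after randomization, and treatment could influence who belongs to them. A comparison within such a subset loses the protection of randomization and answers a different question from a composite that counts death as failure.

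If the programming followed the closing sentences, the co-primary results would be survivor comparisons in a disease for which Protocol 2.6.2.3 gives mortality of 27% to 45%. If only the report followed them, correct numbers would carry the wrong description.

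**Working it through.** The plan states no figure on this point, so the check sets the closing sentences against every rule that produces the primary results.

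**1. How each type of patient is treated**

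| Patient | Closing sentence | Attributes in SAP 4.4.1 | Rule that generates the data |
|---|---|---|---|
| OI: dies before Day 7 | Outside | Included, 90th percentile | SAP 4.10, unfavourable value; Table 3 in 11.1.1, 90th percentile |
| OI: dies on Day 7 without OI | Unclear | Included, 90th percentile | As above |
| OI: reaches Day 7, extubated then, OI not evaluable | Outside | Included, 10th percentile | SAP 4.10, favourable value; Table 3, 10th percentile |
| VFD: dies before or on Day 28 | Outside | Included, 0 days | Table 3, 0 days; Protocol 14.4.11, 0 days |

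SAP 4.10 repeats the death rule in general terms: "Missing data due to death, preventing the collection of the endpoint, will be imputed with an unfavourable value". SAP 7.1.1.1 puts the values assigned to patients who die or are extubated into the OI summaries. Table 3 presents its OI rules as following the estimand definition.

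**2. Who is analysed**

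SAP 4.2.3 and 4.11 place the primary analysis on the randomized set. No rule in 7.1.1.1, 7.1.1.2 or 11.1.1 filters the primary analysis by vital status or ventilation. A programmer following these sections therefore produces the composite analysis, and nothing in them implements the closing clauses.

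**3. Where an alive-and-intubated comparison does appear**

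For OI it is supplementary analysis 7.1.3.6, whose title says that death and extubation are not imputed. SAP 4.11 lists it as a separate addition. The SAP plans no survivor-only VFD analysis.

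**4. Would the distinction matter if the wrong version were computed?**

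This is an illustration for VFD only. Let m be 28-day mortality and μ the mean VFD in survivors, with R for reparixin and P for placebo.

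- Composite difference = (1 − m_R)μ_R − (1 − m_P)μ_P
- Survivor difference = μ_R − μ_P

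The mortality values are the ends of the protocol's 27% to 45% range. Applying them by arm is an assumption, as are the survivor means of 15 and 18 days.

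| m_P | m_R | μ_P | μ_R | Composite difference | Survivor difference |
|---|---|---|---|---|---|
| 27% | 27% | 15 | 18 | 0.73×18 − 0.73×15 = 2.19 | 3 |
| 45% | 45% | 15 | 18 | 0.55×18 − 0.55×15 = 1.65 | 3 |
| 45% | 27% | 15 | 15 | 0.73×15 − 0.55×15 = 2.70 | 0 |

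The two descriptions name different quantities, so it matters which one governs. Steps 1 and 2 show that only the composite is computed. The table measures how far a wrong label could mislead. It does not predict any change in the planned results.

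**5. A neighbouring difference in wording**

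Table 3 requires a patient to reach Day 7 before the extubation value is assigned. The extubation attribute in 4.4.1 and the corresponding bullet in 4.10 do not state this. Read alone, those two could give the 10th percentile to someone extubated and then lost before Day 7. Under Table 3 that OI is missing, and 4.10 sends values missing for any other reason to multiple imputation. Because 7.1.1.1 refers to 11.1.1 for the derivation, the analyst has a definite rule. The closing sentences play no part in it.

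**The case for a change.** The best case for a correction is that these are the only one-sentence statements of the co-primary estimands, so a report would naturally reuse them. The OI sentence closely resembles the target of supplementary analysis 7.1.3.6, so a reader could confuse the primary result with that one. The VFD sentence matches no planned analysis. A definition should not end by contradicting itself, and the correction would cost little.

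Much of this stands. The clash is real on the ordinary reading. One can parse the OI sentence so that being alive and intubated also falls under the word regardless, which would agree with the attributes. That reading is strained, and at best it turns a contradiction into an ambiguity.

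What does not follow is any effect on the analysis. The reporting risk requires an author to lift a sentence while ignoring the attributes directly above it. SAP 7.1.1.1 and 7.1.1.2 refer to section 4.4.1 as a whole, and 7.1.3.6 has its own distinct title. Nothing in the documents says that the clinical study report will use the closing lines alone.

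**Conclusion.** This is a clerical inconsistency and needs no change to the plan. Two trailing clauses, one per co-primary endpoint, disagree with the attributes that define the estimands. The rules for the analysis set, missing data and derivation, together with the protocol's VFD definition, agree with the attributes. Following the plan as written gives the all-randomized composite analysis, and no planned estimate, interval or p-value depends on the two clauses.

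The conclusion assumes that programming follows SAP 4.10, 7.1.1 and Table 3, and that the report describes the estimands by their attributes. If a report did repeat the closing sentences, the numbers would still be those of the composite analysis and only their description would be wrong.
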